3.0 Outcome Measures/Endpoints

3.1 Primary Outcome Measures:

Aim 1: OT will alter alcohol tolerance. Compared to their performance under PL and respective baseline assessment, participants given intranasal OT will show, in one or more of the following, greater alcohol-related perturbation of the subjective response to alcohol, the Stroop test, and Stop Signal task performance.

3.2 Primary Outcome Measures:

Aim 2: OT will reduce motivation for alcohol. Participants will display lower motivation for alcohol under OT compared to PL, reflected by one of more of the following: During alcohol self-administration, less cumulative work for alcohol on the progressive ratio task, and reduced overall alcohol exposure as reflected by the breath alcohol concentration (BrAC) curve during alcohol self-administration; During the BrAC clamp, altered APT derived behavioral economic indices and/or reduced subjective craving for alcohol.

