Session procedures: Self-administration (Figure 4). During the 150 min alcohol self-administration session, the participant initiates each work-set by choosing between 1 of 2 rewards, either alcohol or water. Work-sets consist of trials of the Constant Attention Task, or CAT (Figure 5), developed by our laboratory and with demonstrated sensitivity to pharmacogenomics and sex effects^{38, 39}. Successive rewards require an increasing number of successful CAT trials. The work schedules required to obtain water or alcohol are identical, but progress is tracked separately and not communicated to the participants. Throughout any workset, participants are free to wait, work ad-lib, pause, or cease working. The available rewards are a standardized increment in BrAC (alcohol, labeled "A") or an infusion of saline (water, labeled "W"), each delivered over 2.5 min. Reward delivery begins immediately after the last correct CAT trial required for the work-set is performed. Alcohol reward increments raise the participant's BrAC by 10.0 mg/dL in 2.5 min before declining at a steady rate of -0.8 mg/dl/min, until the next alcohol reward is delivered or as long as pharmacokinetically possible. CAIS continuously estimates the future time course of BrAC and prohibits infusion that would vield a BrAC exceeding the predetermined, ecologically valid safety limit (180 mg/dL in this heavy alcohol drinking sample). The first dose of OT or PL will be administered 30 min before the start of the self-administration phase, and consist of 10 intranasal puffs [insufflations] alternating every 30 seconds between nostrils, delivering in total 40 IU of OT in 1 ml of solution or 1 ml of PL solution. Booster doses of 24 IU of OT will be given approximately hourly after the initial dose. Participants will complete the subjective perceptions assessment and side effects questionnaire prior to the first OT/PL administration, immediately before the start of alcohol self-administration, and at 20 min intervals throughout the session, timed with alcohol reward increments when possible. Except for ad-libitum bathroom breaks, participants remain in the chamber or room for the duration of the experiment; technician interaction is limited to occasional BrAC samples, data collection, and verbal checks to assure subject comfort at the beginning/end of each intervention.

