Figure 5: The CAT task. Subjects initiate the task by pressing down on one of two buttons, labeled "A" (alcohol) or "W" (Water). Holding the button down results in a screen graphic showing the choice button ("A" in this example) surrounded by a yellow circle. When the yellow changes to blue, the subject must release as quickly as possible. On release, the circle returns to white and the subject must indicate whether they thought they were successful. The screen graphic then shows green for successful release, and red for an unsuccessful (too slow) release. The task adapts by increasing the release time window required after errors, and decreasing it after successes. Thus, the percent of successful trials remains constant across subjects and is not affected by basal reaction time, practice, fatigue, or intoxication.

Recovery/Discharge procedures: Alcohol clamp sessions. Upon completion of the alcohol clamp, participants will stay in an inpatient room until they can be safely discharged with a BrAC <35mg/dL. They are served lunch from the ICRC kitchen. Subjects will be told that they should expect to stay at the CRC until 7:00 pm, although they will be dismissed earlier if their BrAC is below 35 mg/dL. Participants with a BrAC > 35 mg/dL at 7:00 pm will be compensated at the rate of \$15/hour in 20-minute increments for the time stayed past 7:00 pm. Participants staying past 5:00 pm will be offered dinner.

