12.0 Statistical Considerations

The primary goal of the study is to generate data that would be supportive of a large, properly powered study of the effects of OT on tolerance and/or motivation for alcohol. For this exploratory study, we anticipate examining within-subject effects of OT compared to PL using paired t-tests, accommodating baseline assessments as appropriate for the specific measures.

Aim 1 Hypothesis Testing Plan

Hypothesis 1: Tolerance to alcohol will be altered by OT, such that participants exhibit greater effects of alcohol when tested with OT compared to PL and each with respect to its own baseline assessment. Specifically, we predict the following differences in one or more of the following measures:

Stop Signal Response Task: Participants will have more rapid reaction times under PL compared to OT. Subjective Perceptions of Alcohol and Craving Participants will report weaker subjective effects of alcohol and higher craving under PL compared to OT. Stroop Test Participants will have shorter response times and fewer errors under PL compared to OT.

Aim 2 Hypothesis Testing Plan

Hypothesis 2: OT will reduce motivation for alcohol as demonstrated by changes in one or more of the following measures:

Alcohol Purchase Task

Participants will display alteration in behavioral economic indices derived from the Alcohol Purchase task under OT compared to PL (for example, a reduction in intensity, greater elasticity, lower breakpoint, lower total outcome, etc.).

Subjective Perceptions of Alcohol and Craving

Participants will report weaker subjective effects of alcohol and higher craving under PL compared to OT. Alcohol Self-Administration

Participants will demonstrate reduced cumulative work for alcohol rewards and less overall alcohol exposure under OT compared to PL.

Missing Data

Missing data may occur intermittently or due to attrition. Due to the within-subjects design, participants completing only one of two experimental sessions will be excluded from final analyses.

Power Analyses

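### The self-administration analysis uses work for alcohol but not the tracked work for water, so a general fall in responding under OT would count as support for Hypothesis 2

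*Combined protocol and SAP*

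**What the plan says.** Section 3.2 gives the self-administration endpoint as "less cumulative work for alcohol on the progressive ratio task", together with lower exposure on the breath alcohol curve. The Aim 2 plan in Section 12.0 repeats both: "Participants will demonstrate reduced cumulative work for alcohol rewards and less overall alcohol exposure under OT compared to PL". The comparison is OT against PL within subject by paired t-test. The rule for support is broad: "OT will reduce motivation for alcohol as demonstrated by changes in one or more of the following measures".

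Section 7.0 (self-administration procedures) describes a two-reward task in which "the participant initiates each work-set by choosing between 1 of 2 rewards, either alcohol or water". On cost and tracking it says: "The work schedules required to obtain water or alcohol are identical, but progress is tracked separately and not communicated to the participants". Effort is voluntary: "Throughout any workset, participants are free to wait, work ad-lib, pause, or cease working". The Figure 5 legend adds that the release window adapts to performance: "Thus, the percent of successful trials remains constant across subjects and is not affected by basal reaction time, practice, fatigue, or intoxication".

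No section names an analysis of water work, of total work, or of alcohol work relative to water work.

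**The concern.** Aim 2 is a claim about motivation for alcohol. Cumulative alcohol work measures that only if a fall in it is not simply part of a fall in all work. Because participants may pause or stop at will, anything that lowers responding in general would lower alcohol work too.

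Alcohol exposure does not corroborate independently. It is built from the alcohol rewards earned, so it falls with alcohol work whatever the cause.

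The rival explanation arises within the protocol's own theory: Hypothesis 1 predicts that OT makes alcohol more impairing. Nor does another behavioural test in the same arm separate the two. Section 5.0 assigns each participant to the clamp or to self-administration, and the Section 8.0 calendar places the Stop Signal and Stroop tests in the baseline, OT/PL and clamp blocks, not in self-administration. Section 12.0 allows for baseline assessments, but no baseline work measure is described for this arm.

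At stake is whether a positive result can be carried into the larger study as an effect on alcohol motivation, or only as reduced responding.

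**Working it through.** The plan gives no alpha, standard deviation, power target or expected count for this endpoint, so there is no figure to reproduce. The check has three parts.

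**1. Which contrasts separate a general fall from an alcohol-specific one?** The PL counts are assumed: 500 alcohol trials and 50 water trials. In both scenarios alcohol work falls 20%, from 500 to 400.

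| Contrast | PL (500/50) | General fall (400/40) | Alcohol-specific fall (400/50) |
|---|---|---|---|
| Alcohol work | 500 | 400 (-20%) | 400 (-20%) |
| Water work | 50 | 40 (-20%) | 50 (0%) |
| Total work | 550 | 440 (-20%) | 450 (-18.2%) |
| Alcohol minus water | 450 | 360 (-20%) | 350 (-22.2%) |
| Alcohol share | 500/550 = 90.9% | 400/440 = 90.9% | 400/450 = 88.9% |
| Alcohol/water ratio | 10 | 10 | 8 |

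The planned measure is the same in both scenarios. Total work and alcohol minus water hardly differ between them, because about 91% of the work is for alcohol. Water work, share and ratio do separate them. Share moves only 2 percentage points because it is near its ceiling. The ratio falls 20%, or ln(8/10) = -0.223 on the log scale.

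**2. How often would a general fall pass the planned test?** Simulation, 20,000 replicates per setting. Assumptions, none from the documents:
- two-sided alpha 0.05;
- within-subject SD of log total work 0.2 or 0.4;
- alcohol share 70%, with within-subject SD of its logit 0.4;
- between-subject SDs 0.5;
- under OT, all work multiplied by (1 - g), preference unchanged.

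From the protocol: at least 5 completers per arm, and 10 to 15 completers in all, so 7 is about half of 15. Entries are the proportion of replicates with significantly lower alcohol work under OT, for SD 0.4 to SD 0.2.

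| General fall g | n = 5 | n = 7 |
|---|---|---|
| 0 | 1.5% to 1.9% | 1.8% to 1.9% |
| 15% | 4.5% to 9.3% | 6.0% to 13.9% |
| 30% | 11% to 31% | 18% to 52% |
| 50% | 32% to 69% | 54% to 92% |

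A paired test of log(alcohol/water) stayed at about 2.5% throughout, the nominal rate in one direction. With a 90% share and n = 5, the 30% fall gave 12% to 39%.

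**3. How precise would the ratio be?** Under the same assumed logit SD of 0.4, the paired difference has SD 0.4 × √2 = 0.566. At n = 5 the standard error is 0.566/√5 = 0.253, and the 95% half-width is 2.776 × 0.253 = 0.70. Since exp(0.70) is about 2.0, the ratio is known only to a factor of two either way. A true change of -0.223 would usually not be distinguishable from none.

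**The case against.** The strongest reply has five parts.

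- **The adaptive task.** A reader might infer that slower reactions under OT would make participants fail trials and so lower their counts. The documents do not support that: the window adapts and the success percentage is said to be unaffected by fatigue or intoxication. This stands. What remains is the amount of work attempted (fewer trials, more pausing, stopping), which the adaptation does not hold constant.
- **Water is already used, and is not a clean control.** A reader might infer that the control condition is wasted. At design level it is not, since it makes alcohol a choice rather than the only activity. The rewards also compete for the same 150 minutes, so water work can rise by substitution when alcohol work falls. This stands, and it limits how much weight the check can bear.
- **Drinking less because alcohol feels stronger may be the hypothesised route.** Sections 1.0 and 2.0 link reversal of tolerance to reduced seeking, and participants start at a breath alcohol of zero, so greater impairment cannot explain the earliest choices. This stands in part. A stronger alcohol effect need not be an artefact, but the planned contrast still cannot tell it from a fall in all responding.
- **Other data exist.** Subjective ratings and side effects are collected every 20 minutes in these sessions. They help, but no analysis links them to work.
- **The study is exploratory.** Section 12.0 says so, and nothing prevents water work from being reported. This lowers the weight of the point. It does not remove it, since Section 2.0 intends evidence for either outcome to be used in a larger study.

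**Conclusion.** The point holds as a gap in interpretation. The plan tests alcohol work and alcohol exposure only; both respond to a general fall in work, and either could support Hypothesis 2 alone. Under the assumed variances, a wholly general 30% fall would pass the test in roughly 1 in 9 to 1 in 3 studies with five completers. These rates rest on assumed counts, variances and a proportional fall. They show what is possible and do not estimate a bias.

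A reader might go further and conclude that a fall in alcohol work would be an artefact, or that cumulative alcohol work is the wrong endpoint. The documents support neither. They contain no evidence that OT suppresses responding in general, and alcohol work is a direct measure of the stated construct. It is also tempting to make unchanged total work, or alcohol minus water, a condition for claiming specificity; the first table shows why neither would serve.

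Given the exploratory purpose and the small arm, the change is worth making but is not critical to the study.

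**What to change.** Keep cumulative alcohol work as the main self-administration measure and add to Section 12.0:

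- The OT-PL paired difference in water work and in alcohol share of work, or in log(alcohol/water), as supportive measures of specificity. State beforehand how zero water work is handled. The log ratio is more sensitive when most work is for alcohol; share remains defined when water work is zero.
- Individual values shown beside the side-effect ratings from the same sessions.
- Reporting language. If alcohol work and alcohol share both fall, describe the fall as alcohol-specific, showing water work so that substitution is visible. If share is unchanged and water work falls similarly, say that reduced general responding cannot be excluded. If water work is near zero, report it descriptively and say that specificity could not be assessed.

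Do not use total work or alcohol minus water as criteria.

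The cost is a few lines of text. No visit, procedure or participant is added, provided that separate tracking of water progress means the counts are stored, which is the natural reading of Section 7.0. The drawback is imprecision: with about five completers and possibly little water work, these measures support interpretation and cannot replace the main outcome. Writing them down before the data are seen keeps the comparator from being chosen afterwards.

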13.0 Statistical Data Management

Primary data will be collected via paper, electronic forms, and computer software output and stored electronically on a department server. The storage location is backed up automatically daily. Other data sources include pathology lab data that will be stored in separate electronic files and merged with the primary data as needed. The following data quality control methods will be used: single entry with random checks of

accuracy, range checks, testing of database by study team prior to moving to data analysis, and regular, periodic extraction and cleaning of data.

14.0 Privacy/Confidentiality Issues

Procedures for protecting privacy interest in the study include advising the participant to ensure his/her privacy during the phone screen and interview if performed electronically, and conducting all further recruiting and testing from or on the Indiana CTSI Clinical Research Center, in a private room during regular hours of operation. Research data is stored either in a lockable file cabinet in a locked and secured area, or on password protected network file servers.

15.0 Follow-up and Record Retention

We expect project completion no later than December 2022. The identifiable project participant files will be destroyed at the conclusion of data analysis. The records will be kept for 7 years after completion of the study. The databases will be kept on a secure server in password-protected files. The database files will be over-written with null data at the completion of the retention interval.

